5. Request for waiver of HIPAA authorization: (When requesting a waiver of HIPAA Authorization for either the entire study, or for recruitment purposes only. Note: if you are collecting PHI as part of a phone or email screen, you must request a HIPAA waiver for recruitment purposes.)

Choose one:

For entire study

For recruitment/screening purposes only

For inclusion of non-English speaking subject if short form is being used and there is no translated HIPAA research authorization form available on the University’s HIPAA website at hipaa.yale.edu.

- i. Describe why it would be impracticable to obtain the subject’s authorization for use/disclosure of this data: *Write here*
- ii. If requesting a waiver of **signed** authorization, describe why it would be impracticable to obtain the subject’s signed authorization for use/disclosure of this data: *Write here*

The investigator assures that the protected health information for which a Waiver of Authorization has been requested will not be reused or disclosed to any person or entity other than those listed in this application, except as required by law, for authorized oversight of this research study, or as specifically approved for use in another study by an IRB.

Researchers are reminded that unauthorized disclosures of PHI to individuals outside of the Yale HIPAA-Covered entity must be accounted for in the “accounting for disclosures log”, by subject name, purpose, date, recipients, and a description of information provided. Logs are to be forwarded to the Deputy HIPAA Privacy Officer.

6. Process of Consent/Accent: Describe the setting and conditions under which consent/assent will be obtained, including parental permission or surrogate permission and the steps taken to ensure subjects’ independent decision-making.

Participation in this study will be strictly voluntary, confidential and non-discriminatory. Participants will be enrolled while they are on-site at one of the participating programs. Potential participants will meet with the Research Assistant to discuss participation in the study. If the participant is interested, the Research Assistant will discuss the study with their guardian/parent. We will provide the adolescents and their parents with an age-appropriate description of the study and told about what they might expect. In describing the study to the participant, the purpose of the study will be described as “finding out how kids can make choices that are healthier for them”. In describing the study to the guardian/parent, we will indicate that the study will focus on promoting healthy behaviors in adolescence and on providing strategies to assist adolescents in making decisions about the many challenges they face.

In Phase I we will employ waived consent. Parents who do not wish for their children to participate will contact the project director.

In Phase II we will obtain informed written assent from the participant and written informed consent from their guardian/parent. For interested participants, study enrollment packets will be sent home that include: a study eligibility checklist, an infographic of the study, a parental consent document, and a school-based health center enrollment form (see attached documents). Research staff will work with school personnel to collect completed enrollment packets that consist of a completed and signed parental consent form and a completed and signed school-based health center enrollment form. After the completed study enrollment packet has been received by the study team from the school personnel, the research assistant will check the forms for completeness and the Research Coordinator will subsequently verify their completeness. The Research Coordinator will then turn the completed school-based health center enrollment forms into the school-based health center staff, and keep the school-based health center enrollment verification documents for our records along with the signed parental consent form.

During the first meeting with participants once the study begins, the participants will again be provided with an age-appropriate description of the study and told about what they might expect for the duration of the study. If the participant is still interested, they will then sign an adolescent assent form.

For both phases, if a participant or their guardian/parent indicates that they do not wish to participate, there will be no further involvement in the study. We will also obtain agreement from the appropriate administrator at the participating program.

Additionally, we may ask participants' parents to sign a form (Parent Permission to Photograph) to allow our research staff to take photographs of their teen during game play sessions. Photographs may be used for purposes of the study, including posting them on our websites, play2PREVENT.org, foragirl.com and our social media. Parents do not have to give permission for their teen's photograph to be used and may request that the pictures be removed at any time if they do agree. Parents will also be informed that not agreeing to allow their teen to be photographed does not affect their teen's participation in the study.

7. Evaluation of Subject(s) Capacity to Provide Informed Consent/Assent: Indicate how the personnel obtaining consent will assess the potential subject's ability and capacity to consent to the research being proposed.

This research does not involve subjects with limited decision-making capacity. Parents and adolescents will be provided with an age-appropriate description of the study and told about what they might expect. In describing the study to the participant, the purpose of the study will be described as “finding out how kids can make choices that are healthier for them”. In describing the study to the guardian/parent, we will indicate that the study will focus on promoting healthy behaviors in adolescence and on providing strategies to assist adolescents in making decisions about the many challenges they face. For focus groups, we will employ waived consent. Parents who do not wish for their children to participate will contact the project director. For pilot-testing and the Randomized

Controlled Trial, we will obtain informed written assent from the participant and written informed consent from their guardian/parent.

8. Non-English Speaking Subjects: Explain provisions in place to ensure comprehension for research involving non-English speaking subjects. If enrollment of these subjects is anticipated, translated copies of all consent materials must be submitted for approval prior to use.

Non-English speakers will not be able to participate in the research project. However, parental information sheets and consent forms will be translated into Spanish for parents of adolescents.

As a limited alternative to the above requirement, will you use the short form* for consenting process if you unexpectedly encounter a non-English speaking individual interested in study participation and the translation of the long form is not possible prior to intended enrollment? YES NO

Note* If more than 2 study participants are enrolled using a short form translated into the same language, then the full consent form should be translated into that language for use the next time a subject speaking that language is to be enrolled.

Several translated short form templates are available on the HRPP website (yale.edu/hrpp) and translated HIPAA Research Authorization Forms are available on the HIPAA website (hipaa.yale.edu). If the translation of the short form is not available on our website, then the translated short form needs to be submitted to the IRB office for approval via modification prior to enrolling the subject. *Please review the guidance and presentation on use of the short form available on the HRPP website.*

If using a short form without a translated HIPAA Research Authorization Form, please request a HIPAA waiver in the section above.

9. Consent Waiver: In certain circumstances, the HIC may grant a waiver of signed consent, or a full waiver of consent, depending on the study. If you will request either a waiver of consent, or a waiver of signed consent for this study, complete the appropriate section below.

Not Requesting any consent waivers

Requesting a waiver of signed consent:

- Recruitment/Screening only (if for recruitment, the questions in the box below will apply to recruitment activities only) For Phase I and Focus Groups in Phase II
- Entire Study (Note that an information sheet may be required.)

For a waiver of signed consent, address the following:

- Would the signed consent form be the only record linking the subject and the research? YES NO
- Does a breach of confidentiality constitute the principal risk to subjects? YES NO

OR

- Does the research pose greater than minimal risk? YES NO
- Does the research include any activities that would require signed consent in a non-research context? YES NO

Requesting a waiver of consent:

- Recruitment/Screening only (if for recruitment, the questions in the box below will apply to recruitment activities only)
- Entire Study

For a full waiver of consent, please address all of the following:

- Does the research pose greater than minimal risk to subjects?
 - Yes *If you answered yes, stop. A waiver cannot be granted.*
 - No
- Will the waiver adversely affect subjects' rights and welfare? YES NO
- Why would the research be impracticable to conduct without the waiver? *Write here*
- Where appropriate, how will pertinent information be returned to, or shared with subjects at a later date? *Write here*

SECTION IV: PROTECTION OF RESEARCH SUBJECTS

Confidentiality & Security of Data:

1. What protected health information (medical information along with the HIPAA identifiers) about subjects will be collected and used for the research?

Names, telephone phone numbers, addresses, email addresses, parent/guardian names, parent/guardian phone numbers, and parent email addresses will all be collected.

2. How will the research data be collected, recorded and stored?

Data collection and management: All data collected from the study assessment questions will be entered directly into the secure web-based system, Qualtrics. Qualtrics is a Yale University supported system that collects and analyzes survey data. Participants will complete their study assessment questions via a link on their individual iPads or cellphones. Their answers will automatically be uploaded from the portable device onto the Qualtrics system.

Additionally, the web-based Oncore database will be used to store participant contact information, randomize participants, and assist with managing follow-up assessment dates. A copy of assessment data will be pulled from Qualtrics for each participant and attached to the participant's file in Oncore. This method limits data entry-associated errors.

The first set of assessments will be conducted at baseline and will collect the most data; subsequent assessments will be conducted at follow-up intervals. Each assessment will require approximately 30 minutes of the participant's time. In addition, data for this study is collected via the videogame software during the participant's game play and will be stored in a secure database.

Furthermore, to collect data on the study's primary outcome of increasing HIV testing and counseling in this age group, school-based health center staff will utilize a password protected Excel form that is on a flash drive to track students who utilized the SBHC over the duration of the project. This password protected flash drive will be kept in a secure locked cabinet in the school-based health center.

3. How will the digital data be stored? CD DVD Flash Drive Portable Hard Drive Secured Server Laptop Computer Desktop Computer Other
4. What methods and procedures will be used to safeguard the confidentiality and security of the identifiable study data and the storage media indicated above during and after the subject's participation in the study? Confidentiality will be protected by having records identified by code number only with the master list including names kept in a sealed envelope in a locked file in the Principal Investigator's office. Data collection and storage will be conducted according to standardized protocols. All information will be identified by code and not linked to subject name except as described above. All data analyses will be performed under approved HIC protocols.

All portable devices must contain encryption software, per University Policy 5100. If there is a technical reason a device cannot be encrypted please submit an exception request to the Information Security, Policy and Compliance Office by clicking on url <http://its.yale.edu/egrc> or email [contact]

What will be done with the data when the research is completed? Are there plans to destroy the identifiable data? If yes, describe how, by whom and when identifiers will be destroyed. If no, describe how the data and/or identifiers will be secured. Data collected in the study will reside in our computerized database and electronic storage mechanisms. All data analyses will be performed under approved HIC protocols.

- 1.
2. If appropriate, has a Certificate of Confidentiality been obtained? *Write here*

SECTION V: POTENTIAL BENEFITS

Potential Benefits: Identify any benefits that may be reasonably expected to result from the research, either to the subject(s) or to society at large. (Payment of subjects is not considered a benefit in this context of the risk benefit assessment.)

It is anticipated that the young adolescents enrolled in this study should benefit directly from the study as the purpose of the study is to improve their attitudes, intentions, and knowledge, and decision-making around health promotion and HIV testing and counseling. It is hypothesized that the participants enrolled in the pilot testing of the adapted PlayForward game will have lower rates of initiation of tobacco use at the follow-up periods. This research has the potential to benefit a large number of kids around the country and worldwide, because if in the pilot test the intervention is shown to be effective, then this program can be replicated elsewhere and with a greater ease of dissemination. The potential benefits to participants are great and strict precautions are being taken to protect the confidentiality and well-being of participants, as has been described above. Thus the potential benefits to the participants outweigh the potential risks.

SECTION VI: RESEARCH ALTERNATIVES AND ECONOMIC CONSIDERATIONS

1. **Alternatives:** What other alternatives are available to the study subjects outside of the research?
No participation in the study
2. **Payments for Participation (Economic Considerations):** Describe any payments that will be made to subjects, the amount and schedule of payments, and the conditions for receiving this compensation.

Phase I: Each participant will receive a \$30 gift card for participating in the focus group. Participants will be provided compensation for completion of the baseline assessments (\$30 gift card), and assessments at 3 and 6 weeks (\$35 gift cards for each set of assessments). The total possible compensation for this stage of the study is \$100 per participant.

Phase II: Each participant will receive a \$25 gift card for participating in the focus group. For those participants in the randomized controlled trial, participants will be provided compensation for completion of the baseline assessments (\$35 gift card), and assessments at 4 weeks (\$20 gift card), 3 months (\$20 gift card) and 6 months (\$35 gift card). The total possible compensation for this stage of the study is \$110 per participant.

Stakeholders who participate in the one-on-one interviews will receive a \$20 gift card.

Key staff members at each school based health center at each of our partner sites will potentially receive a stipend for in school assistance with this study.

3. **Costs for Participation (Economic Considerations):** Clearly describe the subject's costs associated with participation in the research, and the interventions or procedures of the study that will be provided at no cost to subjects.
No costs to subjects will be incurred.
4. **In Case of Injury:** This section is required for any research involving more than minimal risk, and for minimal risk research that presents the potential for physical harm (e.g., research involving blood draws).
 - a. Will medical treatment be available if research-related injury occurs? *Write here*
 - b. Where and from whom may treatment be obtained? *Write here*
 - c. Are there any limits to the treatment being provided? *Write here*
 - d. Who will pay for this treatment? *Write here*
 - e. How will the medical treatment be accessed by subjects? *Write here*

IMPORTANT REMINDERS

Will this study have a billable service? Yes No

A billable service is defined as any service rendered to a study subject that, if he/she was not on a study, would normally generate a bill from either Yale-New Haven Hospital or Yale Medical Group to the patient or the patient's insurer. The service may or may not be performed by the research staff on your study, but may be provided by professionals within either Yale-New Haven Hospital or Yale Medical Group (examples include x-rays, MRIs, CT scans, specimens sent to central labs, or specimens sent to pathology). Notes: 1. There is no distinction made whether the service is paid for by the subject or their insurance (Standard of Care) or by the study's funding mechanism (Research Sponsored). 2. This generally includes new services or orders placed in EPIC for research subjects.

If answered, "yes", this study will need to be set up in OnCore, Yale's clinical research management system, for Epic to appropriately route research related charges. Please contact [contact]

Are there any procedures involved in this protocol that will be performed at YNHH or one of its affiliated entities?

Yes No

If Yes, please answer questions a through c and note instructions below.

- Does your YNHH privilege delineation currently include the **specific procedure** that you will perform? Yes No
- Will you be using any new equipment or equipment that you have not used in the past for this procedure? Yes No
- Will a novel approach using existing equipment be applied? Yes No

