In Phase I of this protocol, we build on the considerable work we have accomplished with the parent grant (R01 HD062080, PI: [name]). Working with the multi-disciplinary team of the play2PREVENT (p2P) Lab, we will conduct the formative work with our target audience and content experts to modify PlayForward for a focus on promoting HTC. We will refine the conceptual model we developed in the earlier project¹³ to promote HTC using constructs from the theory of planned behavior, social learning and self-efficacy theories^{14,15}, and principles from message framing¹⁶ grounded in prospect theory¹⁷.

To this end, our specific aims for Phase I of this protocol targeting HTC in 15-18 year old adolescents are to:

Aim 1: Translate our culturally and socially-tailored videogame PlayForward to focus on HTC in an older age group of 15-18 year old boys and girls by:

- Developing a conceptual model of the theoretical mechanisms of behavior change to be applied specifically within the game. We will develop this model with input from 4 focus groups of 5 adolescents each (n = 20, aged 15-18) and the extant literature.
- Informing the development of a set of intervention manuals (“Game Playbooks”) targeting the new outcome.

Aim 2: Modify aspects of the PlayForward game to reflect this new focus by pilot testing it with 30 adolescents, aged 15-18 to determine in a pre-post design:

- c. The intervention's acceptability and feasibility using self-report data on the game play experience.
- d. Preliminary evidence of the efficacy of the intervention by collecting data on i) intentions to seek HTC; ii) actual obtaining of HTC; and iii) knowledge about HIV/AIDS.

Phase I of this protocol will serve as the foundation for a subsequent Phase II that will undertake full development of the proposed game with the potential of impacting the health and future of adolescents by increasing rates of HIV testing and counseling in a manner that is engaging and compelling and holds the promise of significant reach, dissemination, and impact.

The **specific aims** for Phase II of this protocol are to:

Aim 3: Further adapt and expand our culturally and socially-tailored videogame ***PlayTest!*** to have a greater focus on HTC in addition to HIV prevention in an older age group of 14-18 year old boys and girls by:

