4. **Research Plan:** Summarize the study design and research procedures using non-technical language that can be readily understood by someone outside the discipline. **Be sure to distinguish between standard of care vs. research procedures when applicable, and include any flowcharts of visits specifying their individual times and lengths.** Describe the setting in which the research will take place.

Overview of study design for Phase I

Phase I of the proposed study will be conducted over a six-month period. During months 1-3, we will collect data necessary for game adaptation from our target audience. We will refine our logic model¹³ for the proposed game with input from 4 focus groups of 5 adolescents each (n = 20), aged 15-18, and create a series of behavior change gameplay manuals (“Game Playbooks”⁸⁵) and storyboards (Aim 1). During months 4-6, we will adapt key components of the current PlayForward game on the iPad tablet to focus on HTC in boys and girls (yielding the new game PlayTest!), aged 15-18. We will pilot test it with 30 adolescents, aged 15-18 to determine in a pre-post design the intervention’s acceptability and feasibility using self-report data on the game play experience and collect preliminary data on the efficacy of the intervention in terms of intentions to seek HTC, actual HTC, and knowledge about HIV/AIDS (Aim 2). Given our team’s experience conducting this type of formative work and pilot testing, we are confident that this timeline is feasible.

Study sites: Recruitment/enrollment and conduct of this study will take place at one of the community high school programs with which we already have partnerships (e.g., Wilbur Cross High School; see Letter of Support). Our team has a consistent presence onsite and now has close working relationships with the program staff that are fully engaged in the recruitment process.

Procedures and design

Stage 1: Preliminary videogame adaptation

Conduct focus groups (4 focus groups of 5 adolescents each):

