Measures: We will collect data on participant demographics at baseline. We will collect data on satisfaction with game play/acceptability and feasibility at the end of the 3 weeks of gameplay, and in-game data collected by the new PlayForward game software during gameplay sessions⁸⁹. At baseline, 3, and 6 weeks, we will collect data on intentions to get HIV testing and counseling⁹⁵, HIV/AIDS Knowledge (HIV-KQ)⁹⁶, and other HIV education (including other education about or promotion of HTC) received. Participants will be provided compensation for completion of the baseline assessments (\$30 gift card), and assessments at 3 and 6 weeks (\$35 gift cards for each set of assessments). The total possible compensation for this stage of the study is \$100 per participant.

Assessment Questions	Baseline	3-Weeks	6-Weeks
Demographics	X		
Intentions around HIV Testing/Counseling	X	X	X

HIV/AIDS Knowledge	X	X	X
Other HIV/AIDS Education Assessment	X	X	X
Gameplay Experience		X	

Data analysis strategy: Baseline participant characteristics as well as assessment items (quantitative and qualitative) used to assess acceptability and feasibility of the intervention will be analyzed using descriptive statistics (quantitative data) and thematic coding (qualitative data). We will conduct a longitudinal analysis from baseline across 3- and 6-weeks to examine changes in i) intentions to seek HTC; ii) rates of HTC; and iii) knowledge about HIV/AIDS. In general, we will use two-tailed tests and p-values smaller than 0.05 will be considered to indicate statistical significance. When necessary, however, we will use appropriate adjustment of the level of significance (alpha) to account for multiple statistical tests. All of these analyses will be exploratory given the study sample size. Findings from these analyses in combination with the acceptability and feasibility assessments will be critical in informing the sample size needed to provide power to detect significant differences between the game and a control condition in a subsequent full-scale randomized trial to be conducted through a Phase II proposal. The product and data that result from Phase I will be used to prepare for Phase II.

Overview of study design for Phase II

Phase II will be conducted over the course of two years.

Stage 1: Videogame adaptation (Aim 1), establishment of web-based system and work with implementation and commercialization partners (Aim 2)

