Phase I Data analysis strategy: Baseline participant characteristics as well as assessment items (quantitative and qualitative) used to assess acceptability and feasibility of the intervention will be analyzed using descriptive statistics (quantitative data) and thematic coding (qualitative data). We will conduct a longitudinal analysis from baseline across 3- and 6-weeks to examine changes in i) intentions to seek HTC; ii) rates of HTC; and iii) knowledge about HIV/AIDS. In general, we will use two-tailed tests and p-values smaller than 0.05 will be considered to indicate statistical significance. When necessary, however, we will use appropriate adjustment of

the level of significance (alpha) to account for multiple statistical tests. All of these analyses will be exploratory given the study sample size. Findings from these analyses in combination with the acceptability and feasibility assessments will be critical in informing the sample size needed to provide power to detect significant differences between the game and a control condition in a subsequent full-scale randomized trial to be conducted through a Phase II proposal. The product and data that result from this Phase I project will be used to prepare a Phase II STTR application.

Phase II Data analysis strategy: All statistical analyses will be conducted based on the “intent-to-treat” principle, through the use of either SPSS or SAS statistical packages.

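### Phase I plans to analyse change in actual HIV testing (HTC), but lists no measure of testing obtained at any of its three assessments

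*Combined protocol and SAP*

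**What the plan says.** **What Phase I promises.** Aim 2d, in the opening statement of aims, says preliminary efficacy will be judged by "collecting data on i) intentions to seek HTC; ii) actual obtaining of HTC; and iii) knowledge about HIV/AIDS". Item 2 (Probable Duration of Project) and item 4 (Overview of study design for Phase I) both repeat actual HTC as a pilot outcome. The opening rationale also lists an effect on actual testing rates among the things Phase I is after. The analysis paragraph in item 4 (Phase I, Data analysis strategy) plans a longitudinal analysis from baseline across 3 and 6 weeks "to examine changes in i) intentions to seek HTC; ii) rates of HTC; and iii) knowledge about HIV/AIDS". Item 13 (Statistical Considerations, Phase I) repeats the same three outcomes.

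**What Phase I collects.** The Measures paragraph in item 4 reads "At baseline, 3, and 6 weeks, we will collect data on intentions to get HIV testing and counseling", and goes on to HIV/AIDS knowledge and "other HIV education (including other education about or promotion of HTC) received". Demographics are taken at baseline only and gameplay experience at 3 weeks only. The game software logs in-game data. The table row nearest to testing is "Intentions around HIV Testing/Counseling".

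**The concern.** An outcome that is promised and given an analysis, but has no listed measurement, cannot be reported by someone who follows the plan. A reader of the aims would expect a pilot testing rate at three time points, and a team following the assessment table would have none to give.

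Items 4 and 13 also say that Phase I findings will be critical to sizing the later randomised trial, whose primary outcome was originally testing within six months. A reader could therefore assume that a pilot testing rate exists and was used. What is at stake is agreement between aims, measures and analysis, and an accurate account of what the pilot could contribute.

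**Working it through.** No arithmetic applies to the main point, and the plan gives no Phase I figure to reproduce (the 30 is stated without derivation). The check matches each planned longitudinal outcome to the listed data sources.

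| Phase I outcome (Aim 2d; items 4 and 13) | Baseline | 3 weeks | 6 weeks | Listed source |
|---|---|---|---|---|
| Intentions | yes | yes | yes | Intentions questions |
| Actual HTC / rates of HTC | none | none | none | None listed |
| HIV/AIDS knowledge | yes | yes | yes | HIV-KQ |

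Two of the three outcomes have a source at 3 of 3 time points. The third has one at 0 of 3.

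Other places where testing data might come from:

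1. **Other HIV education.** This item is defined as "other HIV education (including other education about or promotion of HTC) received". It captures exposure to messages about testing, not receipt of a test.
2. **Intentions.** Aim 2d and the analysis text list intentions separately from testing, so one cannot stand in for the other.
3. **Demographics.** The Phase II form names testing history (item 4, Table 1), but the Phase I text does not. Even if it were included, a baseline-only item cannot show change.
4. **In-game data.** These record player actions, not tests taken outside the game.
5. **School health-centre records.** The tracking forms in item 4 belong to the Phase II trial. The signed clinic enrolment form is a Phase II Stage 2 criterion in item 8 and is not among the Phase I criteria. Section IV (item 2) describes the same tracking without naming a phase, but it matches the Phase II procedure and follows text on randomising participants.
6. **Youth Risk Behavior Survey.** Its HIV-testing questions appear only in the Phase II schedule (Table 1).

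None of these supplies a repeated Phase I measure of testing obtained.

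**Did the gap reach the Phase II sample size?** The inputs under Adequacy of sample size in item 4 are:

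- an effect size of 0.27, from a cited earlier study;
- alpha 0.05 and 85% power, giving 118 per group, so 2 × 118 = 236;
- 80% retention, taken from the original PlayForward game, so 236 / 0.80 = 295, against a planned enrolment of 296 (148 per arm).

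No Phase I figure enters.

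**The case against.** The strongest reply is that little was lost.

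- **Precision.** With 30 participants the pilot could say little about a testing rate. If 0 of 30 were tested, the exact two-sided 95% upper limit is 1 − 0.025^(1/30) = 11.6%. An illustrative 3 of 30 gives about 2% to 27%. With no control arm there is no between-group effect to estimate, and the plan calls all Phase I analyses exploratory. This stands, and it limits the weight of the point.
- **Emphasis.** The opening rationale makes increased intentions the primary Phase I outcome, and intentions are measured at all three assessments. This also stands.
- **Questionnaires not shown.** The Phase I table gives domain headings, and in Phase II testing questions sit under broader headings. A reader might infer that no testing question was ever asked in Phase I. The documents support only that none is listed.
- **Timing.** The Phase II focus-group text in item 4 refers to formative work already accomplished in Phase I. The COVID-19 analysis plan in item 13 counts trial participants who had reached 3 months (237) and 6 months (135) unaffected by the pandemic. Phase I therefore appears to be over, and adding an item may no longer be possible. This affects which remedy applies, not whether the texts disagree.

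None of these replies supplies the missing measure or removes the commitment to analyse it.

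**Conclusion.** The inconsistency is real and small. One of the three efficacy outcomes in Aim 2d has no listed data source at any of three time points, for all 30 pilot participants. Intentions, knowledge, and the acceptability and feasibility part of Aim 2 are covered.

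A reader might infer three stronger conclusions, and the documents support none of them:

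- **That Aim 2 as a whole cannot be answered.** Only one component is affected.
- **That the randomised trial was sized on missing pilot data.** The sample-size paragraph names other sources for its effect size and retention. The sentence calling Phase I critical to sample size is general and does not single out testing.
- **That the trial itself lacks testing data.** Phase II has its own survey questions and clinic records, and its current primary outcome is attitudes.

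The verdict assumes that the Measures paragraph and table list everything collected in Phase I. If an unlisted questionnaire asked about testing at all three assessments, the remedy is simply to name it.

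**What to change.** **If Phase I can still be changed, or the item was already asked:** list in the Phase I Measures paragraph and table a self-report question on HIV testing obtained at baseline, 3 and 6 weeks. State its look-back period at baseline, and ask about the time since the last assessment at the two follow-ups, because a rate needs a defined period. The cost is one question at three existing assessments, or one added table row if it was already asked.

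**If Phase I finished without it, as the later text suggests:** withdraw actual HTC and rates of HTC as a Phase I outcome everywhere they appear:

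- the opening rationale;
- Aim 2d;
- item 2;
- the Phase I overview in item 4;
- the Phase I data analysis strategy in item 4;
- its repeat in item 13.

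Amending only Aim 2 and the two analysis paragraphs would leave the contradiction standing in the other three places. In items 4 and 13, limit the statement that Phase I findings inform the sample size to the outcomes actually measured. The cost is a text correction, with no effect on the trial's conduct or analysis.
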